#### **Measures:**

Assessments will be conducted by a Research Assistant trained to administer the study measures.

**Diagnosis:** Baseline diagnostic assessment of bipolar disorder will be verified with a standardized diagnostic scale, Mini-International Neuropsychiatric Interview 7.0.2 (MINI)(Sheehan et al., 1998).

#### **Adherence:**

**a. Tablets Routine Questionnaire (TRQ) for antihypertensives and BD medications separately:** This self-report measure identifies non-adherence for the past 7 and past 30 days (Scott & Pope, 2002a, 2002b), by measuring the percentage of days with missed doses of a given medication. Adherence will be assessed for each regularly scheduled antihypertensive prescribed for  $\geq 3$  months. For individuals who are on more than one medication, an average TRQ will be calculated for all antihypertensive medications. Adherence will then be assessed for each evidence-based BD regularly scheduled maintenance medication (lithium, anticonvulsant, antipsychotic) prescribed for  $\geq 3$  months. For individuals who are on more than one medication, an average TRQ will be calculated for all BD medications. According to our study team’s recent work, the correlation between a single “index” drug and all BD drugs was 0.95 providing support for measuring one medication as proxy for medication adherence(M. Sajatovic et al., 2015). PRN medications will not be included for either hypertension or BD.

**b. eCAP:** Study participants will be given an eCAP device for one of their pill bottles, which will record time/date of bottle opening. eCAP will be used for the antihypertensive medication that the patient missed the most frequently in the past week (in the case of multiple antihypertensive medications missed the same proportion of times, the medication dosed most often will be chosen). This method was chosen over monitoring all medications to limit burden, and is appropriate since eCAP is used to confirm the TRQ. A dose will be counted as “taken” if the bottle is opened within six hours of the prescribed time. We will calculate a percent of doses taken by dividing the number of times the bottle is opened by the number of times it should have been opened as per the prescription. Participants who use organizers rather than bottles will be instructed to open and then shut an empty bottle with an eCAP as a “diary” each time they open their pill organizers. Participants will be given the eCAP at the screening visit if they fit inclusion/exclusion criteria. eCAP will be assessed at the baseline visit based upon pill-taking behavior during the interval between screening and baseline visit. Baseline visits will be targeted at 4 weeks after completion of the screening visit. At screening, participants will be asked when their index drug is up for a refill. They will then be reminded to refill their index drug and fill their eCAP via the iTAB-CV system.

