The Attitude-Social Influence-Efficacy (ASE) model (De Vries & Mudde, 1998) frames adherence to medication as deriving from attitudes (A), social influence (S), and self-efficacy (E). However, adherence also requires intact prospective memory, the ability to remember to do a behavior in the future, which tends to be impaired in those with BD (Bogner, de Vries, O'Donnell, & Morales, 2013; Lee et al., 2010; Zogg, Woods, Saucedo, Wiebe, & Simoni, 2012). Given this deficit, even when an individual has the intention to take medication, they lack the planning or organizational abilities to do so consistently (Zogg et al., 2012). Thus, in order to change and sustain medication adherence in this and similar populations, one must address both ASE and prospective memory. This m-Health intervention primes habit formation by targeting behavioral intention using customized psychoeducational and motivational texts with social reference followed by contextual cues, reminders, and immediate positive reinforcement, to create a strong and automatic habit of taking medication which will be sustainable despite variability over time in behavioral intent.

[figure not shown]

Figure 1: Diagram of expanded ASE model

This study aims to test the feasibility, acceptability and effectiveness of a customized m-Health texting intervention built on the Individualized Texting for Adherence Building (iTAB) platform on antihypertensive adherence and systolic blood pressure in hypertensive persons with BD. This practical, customized intervention, intended to improve adherence to antihypertensives and BD medication among high risk individuals, will be suitable for implementation in either primary care or mental health settings and may reverse the unacceptably high morbidity and mortality in this population.

This study has one specific aim:

**Specific Aim 1:** To test the acceptability, feasibility and effectiveness of iTAB-CV to improve adherence to antihypertensives based on self-reported Tablets Routine Questionnaire (TRQ) and a medication event monitoring system (eCAP).

**Hypothesis 1:** iTAB-CV will improve adherence to antihypertensives in non-adherent persons with BD and HTN.

**Hypothesis 2:** Participants will respond to at least 75% of text messages.

**Hypothesis 3:** At least 75% of participants will find iTAB-CV acceptable based on exit interviews.

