The study requires that participants receive medication reminders to take medications as well as answer daily questions about their mood on their mobile device. If a participant chooses to store personal information on this device, it is possible that if the device were lost, the confidentiality of the participant may be compromised. It is possible that participants could put personal information on the device that could link to the delivered text messages, but the risk of losing confidential information in this way is exactly the same as the risk incurred by owning and using any cellular phone. The text messages used in this study are not specific to bipolar disorder and are purposefully generic. Reminders do not use medication names but rather category of medication (high blood pressure medicine or bipolar medicine) and the mood question is generic. While participants in the patient focus groups indicated that they prefer to have the text messages use the actual name or their disorder, participants will have the option of choosing an alternative name if they wish. The text messages will be delivered from a generic phone number that will not be linked to the specific study goals.

If the phone were to be lost, persons could find responses to medication and mood queries. This will be clearly articulated to participants as a study risk and is specified in the consent document. If participants are uncomfortable with this risk, they may choose not to enroll in the study.

Participants will have their blood pressure taken 4 times over a 12-week period. There is minimal risk to blood pressure readings.

The study requires the participant to place a device on top of a standard pill bottle which may compromise the use of pill organizers or other devices to manage their medications. This may affect their medication adherence.

Participants may choose not participate in the study and this will not in any way affect their regular care with clinicians. Individuals who do choose to participate in the study will continue to receive treatment as usual from their regular care provider(s).

It is possible that the subjects' physical or mental health may worsen during their participation. Subjects will be in close communication with the research study team to make sure they are monitored for unexpected worsening and that the appropriate measures are taken.

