If serious and unexpected adverse events occur, or any other unanticipated problems involving risks to subjects or others, the IRB will be notified. This notification will indicate what serious adverse events were noted, whether they appeared related to the trial, and whether the trial was approved to continue. If found to be related to the trial, the PI will institute appropriate procedures, notify the NHLBI Project Officer, and report such events to appropriate institutional officials and the Office for Human Research Protections.

**Data Analysis plan:** The aim of this project is to test the use of iTAB-CV in a pilot feasibility, acceptability and preliminary efficacy study in a sample of 38 individuals with BD and HTN. Hypothesis: iTAB-CV will be feasible to conduct in an outpatient setting, will be acceptable to participants, and will be associated with improved HTN medication adherence among at-risk individuals with BD and HTN. Treatment acceptability/satisfaction will be measured via a self-report questionnaire and feasibility will be evaluated by percentage of texts answered. The primary dependent measure will be treatment adherence of antihypertensives evaluated with Tablets Routine Questionnaire (TRQ). Adherence will also be measured objectively through eCAP. The measurements will be taken at screening, baseline (4 weeks), 8 weeks, and 12 weeks follow-up. Of primary inferential focus is whether there is change in adherence from baseline to 12 weeks. Adherence will be calculated as a proportion of prescribed medications taken in the past week and will be assessed for each regularly scheduled maintenance agent for HTN prescribed for three months or longer on a daily, routine basis. For individuals who are on more than one such agent, adherence will be assessed for each agent and an average will be

calculated. TRQ will be the main adherence measure, but eCAP will also be analyzed and compared with the TRQ. Secondary outcome measures are: Systolic blood pressure, TRQ for antipsychotic and/or mood stabilizers, psychiatric symptoms (BPRS health utilization, Medication Adherence Self-Efficacy Scale - Revised, Self-Report Habit Index (64), Brief Illness Perception Questionnaire, Beliefs About Medicines Questionnaire, AMSQ, treatment acceptability/satisfaction by questionnaire and exit interviews, and feasibility via % texts answered.

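### Empty-bottle eCAP openings by pill-organizer users are a self-kept log, yet the plan pools them with filled-bottle openings and calls the result objective

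*Combined protocol and SAP*

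**What the plan says.** The eCAP paragraph under Measures, Adherence, puts the cap on one antihypertensive bottle. For people who keep their pills in an organizer it makes a special arrangement: "Participants who use organizers rather than bottles will be instructed to open and then shut an empty bottle with an eCAP". The protocol's own term for this arrangement is a diary. One scoring rule covers everyone: "A dose will be counted as “taken” if the bottle is opened within six hours of the prescribed time". There is no separate rule for an empty bottle.

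The same paragraph gives eCAP a confirming role; monitoring a single drug "is appropriate since eCAP is used to confirm the TRQ". The Data Analysis plan states: "Adherence will also be measured objectively through eCAP". It also sets the order of the two measures: "TRQ will be the main adherence measure, but eCAP will also be analyzed and compared with the TRQ". Table 1 lists both under primary outcomes, and Specific Aim 1 names both.

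Main Hypothesis Testing applies a paired t-test to TRQ and to eCAP from baseline to week 12. Secondary Hypothesis Testing adds a TRQ-eCAP correlation and Bland-Altman plots. Neither is split by how the cap was used, and no section records which participants used the empty-bottle arrangement or whether they changed over time.

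**The concern.** In a filled bottle the cap must come off before the pill can be reached. With an organizer, the cap is on a bottle that holds nothing, and opening it is a second step that the participant must remember. A missed opening may mean a missed dose, or a dose taken but not logged. The two uses are different measurements stored in one variable.

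The logging error could also differ between the two periods being compared. Baseline eCAP comes from the run-in, when no texts are sent (Specific Procedures). Week-12 eCAP follows stage 2, which adds cues, reminders and reinforcement at dosing times. The Background says that "adherence also requires intact prospective memory, the ability to remember to do a behavior in the future, which tends to be impaired" in bipolar disorder, and an extra logging step draws on the same faculty. A reminder could prompt an opening that would have been forgotten in the run-in even though the dose was taken. Tiring of the extra step would work the other way. Participants are their own controls, so no parallel arm can remove either effect.

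At stake is the independence of the confirming measure. TRQ is recall-based self-report, and a participant-kept log is weaker corroboration than the plan's wording implies. The plan also says that its estimates will inform a later controlled trial, so a distorted eCAP change would carry forward.

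**Working it through.** **1. The plan's own figure.** The power statement uses a t-test of the baseline to week-12 TRQ difference, 38 participants, 25% attrition, effect size 0.549 and two-sided alpha 0.05.
- Completers: 38 × 0.75 = 28.5.
- Paired t-test power from the noncentral t distribution, noncentrality 0.549 × √n: 0.800 at n = 28 and 0.814 at n = 29.

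The stated 0.80 reproduces. It concerns TRQ; the plan states no power for eCAP.

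**2. Size of a logging shift (illustration).** Let f be the share of diary users and x the change in their recorded percentage with no change in doses taken. The pooled mean eCAP change then moves by f × x. The documents give neither f nor x, so the inputs below are assumptions.
- Diary users take 75% of doses throughout. They log 70% of those in the run-in and 90% in stage 2.
- Run-in eCAP: 0.75 × 0.70 = 52.5%. Stage 2 eCAP: 0.75 × 0.90 = 67.5%. So x = 15 points.
- f = 20%: 0.20 × 15 = 3 points. f = 40%: 0.40 × 15 = 6 points.
- Against the 21.7-point change in the power paragraph: 3/21.7 = 14%; 6/21.7 = 28%.

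If logging fell from 70% to 50%, then 0.75 × 0.50 = 37.5%, x = −15, and the same shifts appear with a negative sign.

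**3. Effect on the eCAP test.** Assume zero true change, 28 completers, and an SD of change of 39 points (the prior study's figure, borrowed for eCAP). The chance of p < 0.05, nominally 0.05, becomes:

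| f | x (points) | Shift (points) | Chance, SD 39 | Chance, SD 25 (assumed) |
|---|---|---|---|---|
| 10% | 20 | 2 | 0.06 | 0.07 |
| 20% | 15 | 3 | 0.07 | 0.09 |
| 25% | 20 | 5 | 0.10 | 0.18 |
| 40% | 15 | 6 | 0.12 | 0.23 |
| 50% | 20 | 10 | 0.26 | 0.53 |

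The distortion is slight if few people use organizers and substantial if about half do. Nothing the plan collects would show which case applies.

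**4. Cost of leaving diary users out.**
- 20% excluded: 28 × 0.80 = 22.4, about 22 left; power at 0.549 is 0.69.
- 40% excluded: 28 × 0.60 = 16.8, about 17 left; power is 0.57.
- Half-width of the 95% interval at SD 39, t × 39/√n: 15.1 points at n = 28, 17.3 at n = 22, 20.1 at n = 17.

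**The case against.** The plan has several fair answers.

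- *TRQ is the main measure.* This stands. The power analysis rests on TRQ, and its test does not use the cap.
- *The arrangement is disclosed and a check is planned.* The protocol itself calls it a diary, and the TRQ-eCAP correlation and Bland-Altman plots look for discrepancies. This stands in part: without cap mode on record, the plots cannot link a discrepancy to diary use.
- *The reminders concern taking medication.* The sample text refers to the medicine, and no text is described as mentioning the empty bottle. This stands. An effect on logging is possible but inferred.
- *Any cap can be opened without a dose being taken, and a time-stamped opening is better than 7- or 30-day recall.* Both are true. Diary mode adds a further error: doses taken but not logged.
- *The filled bottle seems to be the default,* since participants are reminded to fill the eCAP. That suggests a modest diary share but does not give it.

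A reader might also see a contradiction with the risk section, which says: "The study requires the participant to place a device on top of a standard pill bottle which may compromise the use of pill organizers". The documents do not support that. One passage warns of a burden and the other provides an accommodation; both can be true.

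**Conclusion.** The point holds as one of labelling and sensitivity analysis on the supporting adherence measure. Followed as written, the plan could report a change in logging habit as objectively measured adherence, and it collects nothing that would reveal this.

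A reader might infer that the eCAP result will be inflated, or that the main hypothesis cannot be tested. Neither follows. The net direction is unknown, since reminders could raise logging and fatigue could lower it. The TRQ test is unaffected. The 3-6 point shift, with a false-positive chance of about 0.07-0.12, depends wholly on the assumed diary share, the assumed logging rates, an SD of 39 borrowed for eCAP, and 28 completers.

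Nor do the documents justify replacing the eCAP test with one restricted to filled-bottle users at both visits. That would select on behaviour after baseline and drop organizer users from a sample meant to be broad. It would also reduce power at effect size 0.549 from 0.80 to about 0.69-0.57 if 20-40% were excluded.

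**What to change.** 1. Add one field at baseline, week 8 and week 12: cap on the filled bottle, or on an empty bottle as a diary, during the interval just ended.
2. Keep the pooled eCAP paired test as planned. Prespecify a sensitivity analysis that repeats it without participants who used diary mode in either the baseline or the week-12 interval, and report the number excluded.
3. Present the TRQ-eCAP correlation and the Bland-Altman plot by mode.
4. In the Data Analysis plan, limit the word *objectively* to filled-bottle data and label diary data as self-recorded.

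The cost is one data field and a few sentences of analysis text. The sensitivity estimate will be less precise: with about 22 to 17 participants left, it should be read for consistency with the pooled estimate, not for its own p-value.

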**Methods:**

**Overview:**

This study will test an adherence intervention (iTAB-CV) delivered via interactive text messaging which first targets behavioral intent and then adds cues/reminders and reinforcement to form the habit of taking antihypertensives in non-adherent individuals with BD. Thirty eight individuals with BD and HTN being treated with evidence-based antihypertensive agents and mood stabilizing or antipsychotic medications who are non-adherent with their HTN medicine will be enrolled. This phase uses a prospective cohort design with participants serving as their own control. We will test the iTAB-CV intervention quantitatively for feasibility and acceptability as well as for efficacy in increasing adherence to antihypertensives, decreasing systolic blood pressure, and increasing adherence to BD medication.

[figure not shown]

Figure 2: Diagram of Phase II Design

All study participants will be followed for a 3-month period. iTAB-CV, delivered via mobile phone, is intended to be a brief adjunct to standard primary care and mental health treatment. All individuals will continue to receive

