Stage two of iTAB-CV includes the addition of customized context cues/reminders and immediate reinforcement for medication taking behavior in addition to 1 daily motivational mood rating. The number of texts per day will be determined based on the number of times a day that medications are prescribed (up to four a day). Assessments that include evaluation of treatment adherence, psychiatric symptoms, health status, self-efficacy for medication taking behavior, illness beliefs, medication attitudes, and habit strength for both antihypertensive and BD medications will be conducted at four time points over a 3-month time period (screening, baseline/week 4, week 8, and week 12). Blood pressure and weight will be measured at each of the four contacts. Height will be measured at screen. Individuals who drop out of the intervention, and who agree, will be followed up with outcomes assessments over the same 3-month time period that they would have been evaluated had they remained in the study. Table 1 outlines the study schedule of events/assessments.

Individuals will receive reminder telephone calls or text messages during the 2 weeks prior to their scheduled appointment. Individuals will be requested to provide three additional contacts who may assist in facilitating contact with the participant should the individual miss follow-up appointments and if difficulty arises in contacting the individual to re-schedule follow-up (for example, change of address or telephone number). In order to optimize study retention, study staff will maintain personal contacts with study participants via greeting/post cards for birthdays and holidays and regular contact for "location checks" between assessment periods.

One month post study completion, the PI or research study staff will call the individual and will administer the TRQ over the phone for bipolar and blood pressure medications.

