Main Hypothesis Testing: A paired t-test will be used to test significance for the TRQ and eCAP adherence outcomes from baseline to 12-week follow-up. Nonparametric tests will also be considered. Secondary Hypothesis Testing: Difference from baseline to 8 weeks, and 8 weeks to 12 weeks will also be analyzed. Corresponding TRQ and eCAP values will be correlated and Bland-Altman plots will be used to help identify discrepancies. Correlations will be computed for change in antihypertensive adherence values versus changes in TRQ for antipsychotic and/or mood stabilizers, medication attitudes, self-efficacy, and habit strength. Exploratory longitudinal mixed models will be used to analyze repeated measurements at baseline, 8 weeks, and 12 weeks. Note that the preliminary analyses and model estimates will inform the future design of a more extensive study involving a controlled trial.

Attrition Analyses: Preliminary analyses will determine factors that are associated with attrition effects. Attrition rates in a current BD adherence study at our institution is < 30%. Differential attrition by key covariates such as age and gender will be examined, such as through log rank tests. Power Analysis: Given the preliminary data from a prior BD adherence study (35), difference in oral medication adherence after treatment was 21.7%. Standard deviation of this difference was 39%, resulting in an effect size of 0.56. We expect to observe a similar if not greater effect size. Using a t-test of difference between baseline and 12 week TRQ, power is 0.80 at two-sided alpha = 0.05 for a sample of 38 subjects to reject a null hypothesis of no change in adherence when effect size is 0.549, and attrition is 25%. The projected sample size should thus provide adequate power to detect expected changes in anti-hypertensive drug adherence levels.

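### Organizer users are told to open the eCAP at every organizer opening, so openings for other drugs can be credited as doses of the index antihypertensive; the two eCAP scoring sentences also need reconciling

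*Combined protocol and SAP*

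**What the plan says.** Combined protocol and SAP, Measures, Adherence, item b (eCAP):

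- One device per participant: "Study participants will be given an eCAP device for one of their pill bottles".
- The bottle is tied to one drug: "eCAP will be used for the antihypertensive medication that the patient missed the most frequently in the past week".
- A dose counts as taken "if the bottle is opened within six hours of the prescribed time".
- The percent is then obtained by "dividing the number of times the bottle is opened by the number of times it should have been opened as per the prescription".
- Organizer users keep an empty eCAP bottle as a diary and open it "each time they open their pill organizers".

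The item gives organizer users no denominator of their own, no cap at 100% and no rule for surplus openings.

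Under Overview, the sample is described as "being treated with evidence-based antihypertensive agents and mood stabilizing or antipsychotic medications", so every participant has scheduled drugs besides the index drug. Specific Procedures foresees up to four medication times a day when setting text frequency, and both stages of iTAB-CV address bipolar drugs as well as antihypertensives.

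The Data Analysis plan states: "A paired t-test will be used to test significance for the TRQ and eCAP adherence outcomes from baseline to 12-week follow-up". It also plans correlations and Bland-Altman plots of TRQ against eCAP. Table 1 lists eCAP under primary outcomes, while the Data Analysis plan names TRQ as the main adherence measure.

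**The concern.** The diary instruction follows the organizer, whereas the measure is meant to follow one drug. On the natural reading, the denominator is the prescribed openings for the index drug. The numerator, for an organizer user, includes openings made for anything else in the organizer. No misuse is needed: a participant who follows the instruction exactly produces the error.

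The change from baseline to week 12 can be affected as well as the level. The texts also target bipolar drugs. If a participant takes those more regularly and the antihypertensive no more regularly than before, eCAP can still rise.

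At stake are the eCAP paired test, the use of eCAP to confirm self-report, and the eCAP estimates passed on to the planned controlled trial. The device logs when the bottle was opened but not which drug prompted it, so in-window openings cannot be sorted reliably afterwards.

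**Working it through.** **The plan's own figure.** The only computed figure is the power for TRQ. The effect size is 21.7/39 = 0.556, and the plan uses 0.549. With 25% attrition, 38 × 0.75 = 28.5 completers. The noncentral t at effect size 0.549, two-sided alpha 0.05, gives power 0.7997 at n = 28 and 0.814 at n = 29. The stated 0.80 is reproduced. No figure is stated for eCAP.

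**Assumptions (not in the documents).** The index drug is taken once daily. The organizer is also opened once daily, at another time, for a bipolar drug. The index slot is opened on p = 60% of days at both visits. The other slot is opened on q = 60% of days at baseline and 80% at week 12. The two openings are independent within a day. The true change in index adherence is zero.

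**Formulas for an affected participant.**

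- Six-hour rule, one credit per dose, slots 3 hours apart: 1 − (1 − p)(1 − q).
- Six-hour rule, slots 12 hours apart: p.
- Literal opening ratio: p + q.

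| Scoring | Baseline | Week 12 | False gain |
|---|---|---|---|
| Six-hour, 3 h apart | 1 − 0.4 × 0.4 = 84% | 1 − 0.4 × 0.2 = 92% | 8 points |
| Six-hour, 12 h apart | 60% | 60% | 0 |
| Literal ratio | 0.6 + 0.6 = 120% | 0.6 + 0.8 = 140% | 20 points |

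Under the literal ratio, with two slots a day, a participant who never opens the index slot and always opens the other scores 0 + 1 = 100%. If organizer openings match index doses one to one, neither rule inflates the result.

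**Pooled test.** Let s be the share of participants affected in this way. The pooled false gain is s × 8 or s × 20 points. The chance of p < 0.05 with no antihypertensive effect comes from the noncentral t with n = 28 and an SD of change of 39 points, borrowed from the plan's power paragraph.

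| s | Six-hour: mean shift | Rejection | Ratio: mean shift | Rejection |
|---|---|---|---|---|
| 10% | 0.8 | 5.1% | 2 | 5.8% |
| 30% | 2.4 | 6.1% | 6 | 12.3% |
| 50% | 4.0 | 8.2% | 10 | 25.8% |

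If 39 is taken as the SD within each group, so that the mixture adds variance, the ratio column becomes 5.8%, 11.9% and 24.5%. The six-hour column is unchanged apart from rounding.

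**The case against.** The strongest reply is that the six-hour sentence comes immediately before the percent, and the percent is described as one of doses taken. Read together, a dose earns credit once, from an in-window opening, and eCAP cannot pass 100%. A reader might infer from the formula that readings of 120% or 140%, and false-positive rates near 26%, are built into the plan. The documents do not support that, because those figures require the formula to be read without the sentence before it. The formula does count openings rather than credited doses, so the two sentences must be reconciled. In-window misattribution survives either reading.

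A reader might also infer that eCAP is wrong for every organizer user. That is not supported either. A participant who takes everything at one opening, or whose other slots fall outside the window, is unaffected under the six-hour rule. The documents give no organizer share, dosing times or organizer contents. The figure of four times a day governs text frequency, and the Risks section treats a standard bottle as the usual arrangement.

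The assumed case is also constructed. It holds index adherence flat, as a false-positive calculation must. If both drugs rose from 60% to 80%, the six-hour reading 3 hours apart would go from 84% to 1 − 0.2 × 0.2 = 96%. That is a gain of 12 points against a true 20, so the error can also hide benefit. Independence matters too. If missed days coincide as far as possible, the reading is the larger of p and q: 60% then 80%. The level is less inflated, but the false gain is 20 points. These are bounds on an unknown, not estimates.

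Finally, TRQ is the main measure and eCAP confirms it. That stands, and it limits the consequence.

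**Conclusion.** The point holds as a mismatch between the diary instruction and what eCAP is meant to measure, together with two scoring sentences that do not agree. It applies to organizer users who open the organizer at separate times for other drugs.

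On the six-hour reading and the stated assumptions, such a participant reads 84% and 92% against a true 60%, a false gain of 8 points. The pooled false-positive rate is then about 5% to 8% for affected shares of 10% to 50%. The literal ratio gives larger errors, but it is the less natural reading of the two sentences together. The real pooled effect is unknown, because the documents give neither the share of organizer users nor their dosing times.

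A reader might infer that the primary conclusion or the sample size is undermined. It is not: the power calculation and main analysis rest on TRQ, which this instruction does not touch. The eCAP paired test and the TRQ-eCAP agreement analysis are affected, and the instruction should be settled before eCAP data are collected.

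**What to change.** In Measures, Adherence, item b:

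1. Define the percent as the number of prescribed index doses with at least one opening inside the six-hour window, divided by the number of prescribed index doses, with at most one credit per dose. This replaces the two present sentences.
2. Tell organizer users to open the eCAP only when they take the index antihypertensive from the organizer, and not when they open it for other medicines.
3. Record at screening whether an organizer is used and at what times it is opened. Repeat the eCAP analysis without organizer users who open it at other times.

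The cost is one scoring definition, one instruction sentence, one screening item and one sensitivity analysis, with no new visits, devices or participants. The downside is that the instruction in (2) is slightly harder to remember. The Background says prospective memory tends to be impaired in this population, so some index openings may be missed and adherence under-counted. Change (1) alone removes readings above 100% without that cost, but leaves in-window misattribution in place.
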